## 9.1.7 Unanticipated Adverse Device Effects

In the event of a serious (or unanticipated) adverse event, the Investigator will immediately notify the study monitor by telephone. If such an adverse event is being reported after normal working hours, the Investigator will leave a voice message with accompanying report of the AE.

### 9.2 Reporting

## 9.2.1 Adverse Events (AE) and Severe Adverse Events (SAE) Reporting

All serious AEs, whether or not deemed expected or device-related, must be reported to the clinical monitor immediately or within 24 hours by telephone (see contact details below).

Name: [name], Director of Clinical Research

[contact] [name] Email: *[contact]* 

Address: [name]

A written report prepared by the Principal Investigator must follow within seven working days to the clinical

Confidential 17

monitor and should include a full description of the event and sequence.

#### 9.2.2 Device Malfunctions

Each device failure will be assessed for its possible influence on the patient safety. The investigator should contact the manufacturer n case additional information is required in order to understand the possible implications of a device malfunction.

## 9.3 Risk/ Benefit Analysis

#### 9.3.1 Risks

The potential risks for adverse effects of the treatment procedure include but are not limited to mainly to transient edema or erythema in the treated area the following events were also identified as low probability anticipated adverse effects: pain, tenderness, erythema lasting longer than 6 hours, mild to moderate edema lasting more than 6 hours, burn, blistering, crusting, hyperpigmentation, hypopigmentation, scarring, potential damage to hair follicles and loss of hair within the treatment zones and eye irritation. (See Appendix I for Additional Safety Background).

## 9.3.2 Anticipated Benefits

If the subject agrees to participate in this study, she will be contributing to the understanding of the device's impact and the biological processes that are occurring in the different skin layers. This understanding may lead to optimization of the treatment of these devices. In addition the subject may benefit from improvement in skin laxity in the treated areas.

#### 10 Administrative Procedures

#### 10.1 Investigator Selection

The investigator must be of good standing as an investigator, board certified in OBGYN (or appropriate specialty) and knowledgeable in relevant areas of clinical research to ensure adherence to the requirements of the protocol, including the protection of human subjects. Other site personnel must have appropriate research experience and infrastructure to ensure adherence to the protocol and enrollment of sufficient numbers of evaluable subjects. The curriculum vitae (CV) of the Investigator will be maintained in the study files as documentation of previous medical training. The Principal Investigator will sign the signature page of this protocol, agreeing to comply with all applicable regulations and the requirements of this study.

## 10.2 Ethics committee Approval

This study will be conducted in accordance with the International Conference on Harmonization (ICH) Harmonized Tripartite Guideline for Good Clinical Practice (GCP), 1996; the US Code of Federal Regulations (CFR) Title 21 parts 50, 56 and 812; applicable national laws and regulations and the ethical principles that have their origin in the Declaration of Helsinki.

#### 10.3 Informed Consent

Prior to the procedure, the Investigator must explain to each subject the nature of the study, its purpose, expected duration, and the benefits and risks of study participation. After this explanation and before

Confidential 18

entering the study, the subject must voluntarily sign and date the approved Informed Consent form.

## 10.4 Subject Withdrawal/Dropouts

The subjects will be advised in the written Informed Consent form that they have the right to withdraw from the study at any time without prejudice, and may be withdrawn at the Investigator's discretion at any time. In the event that a subject drops out of the study or is withdrawn from the study, the Exit/Termination CRF form should be completed. On the withdrawal page the Investigator should record the date of the withdrawal, the person who initiated withdrawal and the reason for withdrawal.

Reasonable effort should be made to contact any subject lost to follow-up during the course of the study in order to complete assessments and retrieve any outstanding data and study medication/supplies. The records of subjects who terminate prior to completing the study will be retained and the reason for termination will be documented.

The following are possible reasons for subject dropout/withdrawal:

- Adverse event that would prevent subject compliance with the protocol;
- Subject withdrawal of consent;
- Subject lost to follow-up (e.g., subject cannot be located or contacted and does not return for follow-up visits);
- Subject death;
- Investigator requested subject to be withdrawn.

However, every effort should be made to see that subject is followed for the remainder of the study even if subject is unable or unwilling to comply with the protocol.

## 10.5 Case Report Forms (CRFs)/Data Collection

The Investigator is responsible for completely and accurately recording study data in the appropriate sections of the CRFs.

Data recorded on the CRF and photographs will serve as a source document for the study data.

### 10.6 Subject's Financial Compensation

Subjects will not pay for any office visits, examinations and procedures as part of this clinical study.

### 10.7 Device Use/Accountability

The evaluation site personnel will maintain records of the model and serial number of the devices (if appropriate) used for treatment during the conduct of the study.

## 10.8 Training Requirements

Prior to any independent use of the modified Venus Versa (MP) system™, study personnel, will receive proper training from the Venus Versa (MP) Manufacturer clinical training team. Training requirements will be discussed during study initiation and will include site responsibilities, training of device use and study documentation.

### 10.9 Modification of Protocol

The protocol may be amended with the agreement of the sponsor and upon notification of and approval by the IRB or other relevant ethics committees.

Confidential 19

Investigators should review the contents of this protocol. Subsequent alterations should only be made in written conjunction with the sponsor.

Medically significant amendments to the protocol (e.g., changes that increase the risk or the inconveniences for the patient, inclusion of new categories of patients, etc.) must be approved by the local IRB prior to implementation.

## 10.10 Data Retention/Archiving Data

The Investigator must keep the following documents in a secure place for at least two years after the last clearance of a marketing application or at least two years have elapsed since the formal discontinuation of clinical development of the investigational product.

- A signed copy of the final protocol and amendments.
- Copies of the subjects' evaluation forms, data clarification forms and any associated subject-related raw data or where applicable, authorized copies of raw data.
- Clinical photographs stored on CD-ROM or similar electronic media.
- Histopathology slides and molecular assay results.
- The subjects' signed Informed Consent forms.

## 10.11 Site Monitoring

The investigator has the responsibility for monitoring the study according to a monitoring plan.

## 10.12 Reporting Requirements

The investigator bears reporting responsibility per local regulations.

### 10.13 Confidentiality

This study is confidential. All reports, communications and public information relating to study subjects will identify the subject only by his/her trial ID code. The study personnel will complete subject identification on a confidential subject log, which will be used for purposes of subject tracking and follow-up. This will be treated in accordance with strict adherence to professional standards of confidentiality, and will be filed with adequate security and restricted accessibility.

#### 11 Abbreviations and Terms

AE Adverse Event

SAE Serious Adverse Event

EC Ethical Committee

IRB Institutional Review Board

CRF Case Report Form

VAS Visual Analogue Scale

Confidential 20

## 12 Appendixes

## 12.1 Appendix A - Study Flow Chart

## **Study Flow Chart**

	•	\/:a:+ #3	V:-:+ #2	\/:a:+ #4
	V	Visit #2	Visit #3	Visit #4
	Visit #1	4 weeks after	4 weeks after	4 weeks after
Study Activities		Visit #1	Visit #2	Visit #3
·	Screening &Tx1	FU1 and Tx2	FU2 and Tx3	FU3
Qualify for study: Informed Consent, Eligibility assessment, Demographic information, Medical history & treatment related medical examination	Х			
Photographs	Х	х	х	х
PH measurement	х	x	x	x
Histology and Molecular Studies	Х	X	Х	Х
Treatment	Х	Х	Х	
Immediate and short term responses (assessment by investigator)	Х	х	х	
Subject Pain assessment (VAS)	Х	Х	Х	
Subject Duration of Post-Treatment Adverse Events Questionnaire	Х	Х	Х	Х
Subject Treatment Evaluation Questionnaire (v. 4)	Х	Х	Х	Х
Subject's improvement/satisfaction (GAIS)				Х
Concomitant medication	Х	Х	Х	Х
Adverse events recording	Х	Х	Х	Х
Skin improvement assessment by				V
independent evaluators using				X
photographs				

Confidential 21

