## 3 Study Objectives

## 3.1 Primary Objectives

- To evaluate the safety of treating the mons pubis, labia and vaginal introitus with the Freeze Diamondpolar applicator.
- To evaluate the safety of the internal treatment of the vagina with the investigational applicator.
- To verify the efficacy of using the Freeze Diamondpolar applicator for improving general skin appearance of the Mons pubis and Labia including improvement of skin irregularities and skin laxity of the female genitalia and introitus.
- To determine and/or quantify any potential regenerative properties associated with the study treatments.

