#### 6.2.2 pH Paper

The investigative site will ensure pH paper is available for use during this study. pH measurements will be taken at various visits as detailed in the schedule of events chart. For consistency purposes, all pH measurements throughout the study shall be taken from the mid posterior wall of the vaginal mucosa.

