## 6.2.3 Histopathology and Molecular Studies

The investigative site will ensure Tischler biopsy forceps or the equivalent of a small punch biospsy (2-3mm) for skin/mucosal biopsy is available for use during this study. Histopathology and molecular study specimens will be taken at various visits as detailed in the schedule of events chart (Appendix A). For consistency purposes, all histopathology and molecular study specimens taken throughout the study shall be taken from any of the anatomic sites treated.

Subject anonymity will also be assured for histopathology slides and molecular assay results by deleting any associated ID detail. Only the code for the Case Number in the study will appear on the records being transferred to the sponsor.

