## 7 Study Procedures

### 7.1 Study duration and timelines

Each subject will be enrolled and scheduled for three treatments at approximately four week intervals and return for a follow-up visit at one month (± seven days) after the last treatment for evaluation of the treated areas. During each visit various tasks will be performed as detailed in the study flow chart (Appendix A).

Each subject will therefore participate in the study for a period of at least 3 months. The study is anticipated to be completed within six months.

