#### 7.2.1 Post Treatment Responses

Immediate and short term responses (erythema, edema, purpura, etc.) will be assessed by the investigator immediately and up to 30 min post treatment, by a 5 level scale: 1=none; 2=trace; 3=moderate; 4=marked; 5=severe.

In addition, subject reporting on duration of post-treatment adverse events questionnaire will be collected after each treatment and at the follow-up visit.

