## 7.2.4.2 Level of improvement and satisfaction

Subject's Improvement and Satisfaction with treatment will be recorded by using the GAI scale at the last follow up visit (see Appendix B).

Table 1 - Clinical Evaluation Tools

Claim/task	When to conduct?	Tool		
Photography	Baseline, immediately before	Standardized digital photographs		
	treatments 2, 3, FU 3			
Vaginal pH	Baseline, immediately before	Standard pH paper		
	treatments 2, 3, FU 3			
Histopathology & Molecular	Baseline, immediately before	Histology slides, special staining		
Studies	treatments 2, 3, FU 3	and assays.		
Immediate and short term	Immediately following treatments	Examination of skin in the treated		
response evaluation by	1-3	area based on 5 level scale		
investigator		(Appendix F)		
Subject's duration of post-	Before treatments 2, 3, FU 3	Subject Questionnaire on post		
treatment adverse events questionnaire		treatment response (Appendix G)		
Subjects discomfort/pain	Immediately following treatments	VAS (Appendix E)		
assessment	1-3			
Subjects improvement/	FU3.	GAI (see Appendix B)		
satisfaction assessment				
score				
Independent reviewers score	At the end of the study	GAI (see Appendix B)		

Confidential 11

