## 7.7 Follow-up regimen

Follow-up visits will be combined with treatments visits 2 and 3 and an additional follow up visit will occur one month (± seven days) after the last treatment as detailed in Appendix A.

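### Internal vaginal safety is a primary objective, but no mucosal inspection is explicitly scheduled before re-treatment or at FU3, and no form asks about symptoms of delayed vaginal injury

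*Combined protocol and SAP*

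**What the plan says.** Section 3.1 lists as a primary objective "To evaluate the safety of the internal treatment of the vagina with the investigational applicator", and section 8.1 states that the study will confirm that this applicator is safe.

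The assessments that bear on this are:

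- **Medical examination.** Appendix A has one row containing "Medical history & treatment related medical examination", marked at Visit 1 only.
- **Investigator response.** Section 7.5, step 8, has the treated area examined once both the external and internal treatments are finished. Section 7.2.1 says the response "will be assessed by the investigator immediately and up to 30 min post treatment". Table 1 describes the tool as "Examination of skin in the treated" area. Appendix F has one immediate and one short-term score for tissue response, with no site.
- **Follow-up.** Section 7.7: "Follow-up visits will be combined with treatments visits 2 and 3". FU3 is the only visit without treatment. Section 7.1 says that subjects "return for a follow-up visit at one month (± seven days) after the last treatment for evaluation of the treated areas", but Appendix A has no examination row for that visit.
- **Vaginal pH.** Due at all four visits. Under section 6.2.2 the samples "shall be taken from the mid posterior wall of the vaginal mucosa".
- **Biopsy.** Due at all four visits. Under section 6.2.3 the specimens "shall be taken from any of the anatomic sites treated". The Appendix D log has boxes for mons pubis, labia and introitus.
- **Subject forms.** Appendix G asks how long redness, swelling, crusting and blistering lasted, with no site. Appendix H, marked at every visit, includes vaginal tightness, vaginal dryness and sexual satisfaction, each as a current level and as change since before treatment.
- **Adverse events.** Recorded at every visit. Section 9.1 covers what the patient reports or the physician observes.

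**The concern.** A safety conclusion about a treated site is only as good as the plan for looking at that site. For the vagina, the explicit looking stops about half an hour after each treatment. An injury that appears or persists after that would have to be volunteered by the subject, noticed in passing, or inferred from an item written to measure benefit.

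This matters here for three reasons. Appendix I singles out the vaginal epithelium as the tissue most vulnerable to heat damage. The same mucosa is treated again about 4 and 8 weeks after the first session, and no baseline for that day is recorded. Safety in the first 10 patients is to be reviewed by the IRB before the study is enlarged to as many as 300. The interim safety report in section 8.3 draws on data collected just after the first treatment, so it cannot fill the gap. The two-year follow-up of complications in the burn procedure (Appendix I) starts only once a complication has been found.

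**Working it through.** **1. Each instrument against the question: could it show a delayed vaginal injury?**

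| Instrument | When | Site named | Delayed vaginal injury? |
|---|---|---|---|
| Medical examination (Appendix A) | Visit 1 | Not specified | No: a screening step |
| Investigator response (7.2.1, 7.5 step 8, Table 1, Appendix F) | Treatments 1–3, to about 30 min | Treated area (7.5); skin (Table 1); none (form) | Partly, on the Tx2 and Tx3 days, but after that day's treatment; nothing comparable later than Tx3 |
| Photograph grading (Appendix C) | Baseline and follow-up | Mons pubis, labia | No |
| pH (6.2.2) | Visits 1–4 | Vaginal wall | Indirectly: a chemical reading |
| Biopsy (6.2.3, Appendix D) | Visits 1–4 | Any treated site; no vagina box in log | Only if a vaginal site happens to be chosen |
| Pain VAS (Appendix E) | Just after treatments 1–3 | Mons pubis, labia | No |
| Side-effect questionnaire (Appendix G) | Before Tx2, before Tx3, FU3 (Table 1) | None | Weakly: mostly visible signs, which a subject cannot readily see internally |
| Treatment evaluation (Appendix H) | Visits 1–4 | Vagina | Indirectly: dryness, tightness, sexual satisfaction |
| Adverse event recording (9.1) | Visits 1–4 | None | Yes, if volunteered or observed |

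Appendix H also has an open question about sensations such as burning or itching, but it concerns the time during treatment. Its list of conditions (question 9) could not be read in full and is not counted as a gap.

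**2. Count**, with the 10 subjects of section 8.2.

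- Follow-up visits: 10 × 3 = 30, each with a vaginal pH sample due.
- FU1 and FU2, which are also treatment days: 10 × 2 = 20. Mucosal inspections explicitly scheduled before that day's treatment: 0. A response check follows treatment on all 20.
- FU3: 10 × 1 = 10. Mucosal inspections explicitly scheduled: 0, and no response check.

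For an injury from Tx1 or Tx2, the next investigator examination comes about four weeks later and after renewed heating, recorded as a score with no site. An old lesion and a fresh response cannot then be told apart. For Tx3, the last examination with a form is at about 30 minutes.

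**3. What incomplete detection does to the safety statement.** The plan gives no event rate or precision target (section 8.2 rests on previous experience), so there is no figure to reproduce. The following is an illustration.

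With zero observed events in n subjects, the one-sided 95% upper bound is 1 − 0.05^(1/n). For n = 10: 1 − 0.05^(1/10) = 25.9%. If each true event is detected with probability s, the bound on the true rate is 25.9% / s. At a true rate of 10%, the chance of detecting at least one event is 1 − (1 − 0.10 s)^10. The documents give no value of s, so a range is shown.

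| Assumed s | Upper bound, 0 seen in 10 | Chance of at least one detected, true rate 10% |
|---|---|---|
| 100% | 25.9% | 65% |
| 75% | 34.5% | 54% |
| 50% | 51.8% | 40% |
| 25% | above 100%: uninformative | 22% |

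Enlarging the study does not remove the factor 1/s. With n = 300 the bound is 1 − 0.05^(1/300) = 0.99%, and 0.99% / 0.5 = 1.98% at s = 50%.

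**The case against.** The strongest reply is that the plan is not silent about the vagina after treatment.

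- Appendix H is marked at every visit and asks about dryness and tightness compared with before treatment, down to a marked worsening. This stands. A reader might infer that no visit asks about vaginal symptoms at all; the documents contradict that. What remains is that these items measure benefit, and none asks about bleeding, discharge, burning or pain with intercourse after treatment.
- Step 8 of section 7.5 follows both treatments, the vagina is a treated area, and Appendix F speaks of tissue. This also stands. One cell of Table 1 does not prove that the vagina goes unexamined on treatment days, and 20 of the 30 follow-up visits do include an examination of the treated area. Its timing after re-treatment and its score without a site limit its use for delayed injury.
- FU3 has the stated purpose of evaluating the treated areas. True, but no row, method or form carries this out for the vagina.
- The anticipated events in 9.1.6 include pain, burn, blistering and scarring without restriction to external skin, and 9.3.1 is open-ended. So the lists do not show that vaginal events were excluded, and this point does not rely on them.
- Adverse events are recorded at each visit, and an investigator may well look while sampling pH. That is plausible, but the plan neither requires nor records it.

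**Conclusion.** The point holds as a gap in ascertainment. No inspection of the vaginal mucosa is explicitly scheduled at FU1 or FU2 before re-treatment, or at FU3 (0 of 30 visits with 10 subjects), and no form asks about vagina-specific injury symptoms after treatment. Delayed internal injury depends on spontaneous adverse event reports, incidental observation and efficacy-type items. The gap is clearest after Tx3.

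A reader might go further and conclude that the vagina is never examined after treatment or that delayed safety rests wholly on unprompted complaints. The documents do not support that, given the same-day check, Appendix H, pH sampling and possible vaginal biopsies.

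The size depends on detection sensitivity, which the documents do not give. Over an assumed 100% to 50%, the upper bound after no events in 10 subjects runs from 25.9% to 51.8%. The calculation treats subjects as independent, with the same chance of detection for each event. Even with perfect detection, 10 subjects support only a loose statement; incomplete detection loosens it further and is the part that can be changed cheaply.

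**What to change.** 1. **Appendix G:** add vaginal symptom rows, for example bleeding, discharge, burning and pain with intercourse.
2. **Table 1 and Appendix F:** extend the Table 1 description from skin to skin and vaginal mucosa, score the vagina on its own line of Appendix F, and report internal and external findings separately.
3. **Appendix A:** have the investigator record the appearance of the vaginal mucosa on the existing 5-level scale when the pH sample is taken, before any treatment that day and at FU3.

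Items 1 and 2 change forms and wording only. Item 3 adds a few minutes and possibly some discomfort: section 6.2.2 gives the sampling site but not the technique, so visual access at that moment is an assumption to confirm with the site. More minor findings will be recorded. No new visit or assessor is needed. The change concerns assessment and recording only and sets no treatment rule.

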#### 9.1.6 Anticipated Outcome Related Adverse Events

Anticipated adverse events in this study include pain, tenderness, purpura, persistent erythema, edema, burn, blistering, crusting, hyperpigmentation, hypopigmentation, scarring and potential for damage to hair follicles within the treatment area and subsequent loss of hair within the treatment area.

Any anticipated AE that occurs at any time during or after the use of the study device must be recorded by the Investigator. If the anticipated AE, in the opinion of the Investigator, is likely to affect the safety of the subjects or the conduct of the study, the ethic committee will be notified of the effect within 10 working days. In this study if an adverse event occurs the Investigator will continue following the subject until the case is resolved or up to 1 month following the last visit, whichever comes first.

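### No contact is scheduled after the fourth biopsy at Visit 4, so its delayed complications are captured only if the subject reports them

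*Combined protocol and SAP*

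**What the plan says.** - **Biopsy schedule.** Appendix A (section 12.1) marks "Histology and Molecular Studies" at Visits 1, 2, 3 and 4. Table 1 in section 7.2.4.2 agrees: baseline, then "treatments 2, 3, FU 3".
- **What the row means.** Section 6.2.3 names the instrument, "Tischler biopsy forceps or the equivalent of a small punch" biopsy of 2-3 mm, and ties the specimens to the chart: "Histopathology and molecular study specimens will be taken at various visits as detailed in the schedule of events chart".
- **AE schedule.** Appendix A marks "Adverse events recording" at Visits 1 to 4 and has no later column.
- **Last contact.** Section 7.7 combines follow-up with treatment visits 2 and 3 and adds one more: "an additional follow up visit will occur one month (± seven days) after the last treatment". No visit or call comes after it.
- **After the last visit.** Section 9.1 has AEs recorded when the subject reports them or the physician sees them, whether or not they are device-related, and states no cut-off at Visit 4. Section 9.1.6 says that if an AE occurs, "the Investigator will continue following the subject until the case is resolved or up to 1 month following the last visit, whichever comes first".

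**The concern.** Infection, late bleeding or scarring at a biopsy site can appear after the subject has gone home. For the biopsies at Visits 1 to 3 the subject returns and AEs are recorded. For the biopsy at Visit 4 she has left the schedule, and nobody is due to ask her.

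Two things are at stake. The first is the subject: a delayed complication may come to the investigator's notice late or not at all. The second is the AE listing: the synopsis counts AEs over the whole study, and section 9.1 includes those unrelated to the device, so biopsy complications belong in it. Detection is then uneven, planned after three biopsies and dependent on spontaneous reporting after the fourth. The fourth is also the only biopsy with no device treatment scheduled at the same visit, so a site complication after it would be the easiest to attribute to the biopsy rather than to the device.

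**Working it through.** The plan states no figure on this point, so there is none to reproduce. The check sets the schedule rows side by side and then counts.

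**Step 1: schedule (Appendix A, Table 1, section 7.7).**

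| Visit | Biopsy | AE recording at that visit | Next scheduled AE recording |
|---|---|---|---|
| 1 (Tx1) | yes | yes | Visit 2, 4 weeks later |
| 2 (FU1, Tx2) | yes | yes | Visit 3, 4 weeks later |
| 3 (FU2, Tx3) | yes | yes | Visit 4, about 4 weeks later |
| 4 (FU3) | yes | yes | none |

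**Step 2: does another provision supply an enquiry after Visit 4?**
- Section 9.1 records events that are reported or observed. Once visits end, it depends on the subject coming forward.
- Section 9.1.6 sets how long an AE is followed. It covers an event that begins after Visit 4 if it is reported, but it schedules no contact to find one.
- The burn procedure in Appendix I gives at least 2 years of follow-up, but for device complications that have already been identified.
- The Appendix G questionnaire, last used at FU3, asks about redness, swelling, crusting and blistering after treatment. It has no biopsy-site item.

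None of the four starts a contact.

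**Step 3: count.** Assume one specimen per visit (section 6.2.3 does not state the number) and no drop-out.
- Per subject: 1 of 4 biopsies = 25% without a later scheduled AE recording.
- 10 subjects (section 8.2): 10 × 4 = 40 biopsies; 10 × 3 = 30 have a later recording and 10 do not.
- 300 subjects (maximum in sections 2 and 5.1): 300 × 4 = 1200; 900 have one and 300 do not.

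**Step 4: scale.** The documents give no complication rate, so the risk p of a delayed complication per biopsy is an assumption, shown over a range. The chance of at least one event among the 10 final biopsies is 1 − (1 − p)^10:

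| Assumed p | Chance of at least one event |
|---|---|
| 1% | 1 − 0.99^10 = 9.6% |
| 2% | 1 − 0.98^10 = 18.3% |
| 5% | 1 − 0.95^10 = 40.1% |
| 10% | 1 − 0.90^10 = 65.1% |

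These are chances that an event occurs, not that it is missed; a subject may report it.

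If no event were seen, the one-sided 95% upper limit on the risk per biopsy is 1 − 0.05^(1/n). For n = 30 this is 9.5%, and for n = 40 it is 7.2%, treating biopsies as independent although each subject contributes several. Covering the last biopsy therefore tightens the bound only modestly.

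**The case against.** The strongest reply is that the plan does provide for events after Visit 4. Section 9.1 sets no end to recording, and section 9.1.6 requires anticipated AEs, a list that includes pain, tenderness and scarring, to be recorded whenever they arise during or after device use, with follow-up to 1 month past the last visit. Subjects come from the investigator's own patients (section 5.1), which makes a later report to the same clinic more likely. Immediate bleeding could be recorded at Visit 4 itself; the order of biopsy and AE recording within the visit is not stated. The contrast with the earlier biopsies is also softer than the counts suggest. Appendix G has no biopsy item at any visit, so those biopsies rely on the general AE row too. Finally, the safety objectives concern the applicators, and device treatment ends at Visit 3.

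All of this stands, and it rules out three readings that a reader might infer:
- **That AE recording stops at Visit 4.** Only the scheduled row stops; later reports must still be recorded.
- **That every completer's AE record is incomplete.** A record is incomplete only if a delayed complication occurs and goes unreported. The documents give no rate from which to estimate how often.
- **That the device-safety conclusion is undermined.** A complication of a final biopsy, a month after the last treatment, bears little on it.

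What the reply does not supply is a prompt. Every provision it cites waits for the subject to report or the physician to notice. The consent pages are not available for review, so any instruction to report later problems cannot be checked; such an instruction would still not be a scheduled enquiry.

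**Conclusion.** The point holds in a narrow form: the schedule has no contact after the Visit 4 biopsy, so its delayed complications reach the AE listing only through unsolicited reports. The size is 1 of 4 biopsies per subject (10 of 40 at 10 subjects, 300 of 1200 at 300), under the assumptions of one specimen per visit and no drop-out. These are scheduling slots without a later AE recording, not lost data. The main consequence is for subject safety and the completeness of the AE listing; the device-safety conclusion is little affected. It is a cheap improvement rather than a flaw that threatens the study.

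**What to change.** Add one column to Appendix A for a telephone AE contact after Visit 4, within the 1-month period that section 9.1.6 already names, with the day left to the investigator. Have the call ask about the biopsy site as well as AEs in general. Include events found there in the AE listing of section 8.3, marked as following the final biopsy.

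Biopsies with a later scheduled AE enquiry would then rise from 3 of 4 to 4 of 4 per subject: from 30 to 40 of 40 at 10 subjects, or from 900 to 1200 of 1200 at 300. The cost is one short call per subject, 10 calls at 10 subjects and up to 300 at maximum enrolment. No visit or procedure is added, and no treatment or clinical rule changes.
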